This pivotal study was a prospective, multi-center, randomized, double-blinded placebo controlled dual-arm study of 100 subjects, of which 86 passed screening and were available for primary endpoint analysis. Subjects were adults with neck and shoulder pain of musculoskeletal origin (osteoarthritis, chronic muscle spasms and cervical and thoracic spine sprain strain) ongoing for at least 30 days with a recorded 0-100 VAS pain scale rating of 50 or greater. Average duration of neck and/or shoulder pain at study entry was about 6 years. Red laser light therapy was administered to the sagittal suture (top of head); left and right cervical, shoulder and torso areas; right and left shoulders during each of passive external rotation and passive adduction of the arm and shoulder; right and left cervical muscles and trapezius muscles during passive left lateral flexion of the cervical spine; and the right and left sternocleidomastoid and scalene muscles during passive range of motion, for a total of 13 minutes during a single treatment administration. Post-treatment follow-up period was 48 hours.

Primary efficacy success was evaluated immediately following the single device treatment administration relative to baseline as the change in neck and shoulder pain rating as recorded on the 0-100 VAS. Individual subject success was defined as a 30% or greater improvement (decrease) in the primary efficacy measure from baseline to endpoint. Study success was defined as a minimum 30% difference between treatment groups, comparing the proportion of individual successes. 65.1% of actively treated subjects attained individual success compared with 11.6% of control (placebo) subjects, resulting in a 53.5% difference between treatment groups, exceeding the 30% criteria by 23.5% ($p < 0.0001$). Hence the study met its primary efficacy endpoint. Additionally, the magnitude of the mean change in neck and shoulder pain VAS rating at endpoint relative to baseline was -29.02 for actively treated subjects and -4.91 for control (placebo) subjects, a 20.08 difference ($p < 0.0005$). No treatment-related adverse event was reported or observed for any subject throughout study duration, and no other safety issues occurred.

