2. The following Erchonia-sponsored clinical study outcome supported the 510(k) clearance for application of the simultaneous *combined Erchonia red and violet laser light therapy* to the *adjunctive temporary relief of minor chronic neck and shoulder pain of musculoskeletal origin*.

The study was a single (active treatment only) group non-inferiority design to evaluate equivalency or superiority of the Erchonia® EVRL in red/violet diode combination application with red diode only application in the temporary reduction of neck and shoulder pain of musculoskeletal origin. The comparative active data for the Erchonia® red diode only therapy was attained in the 2001 trial whose results successfully supported 510(k) clearance (K012580) of application of the PL3000 red diode only for the identical indication being sought through the results of this clinical trial.

Forty-four (44) subjects completed the study. Subjects were predominantly Caucasian (82%) males (39%) and females (61%) of average age 54.07 years with chronic neck and/or shoulder pain of musculoskeletal origin due to osteoarthritis, chronic muscle spasms or cervical and thoracic spine sprain strain who rated 50 or greater on the 0 to 100 Visual Analog Pain Scale (VAS). Average subject duration of neck and shoulder pain was 76.58 months with the location of pain evenly distributed across the right and left sides. Average VAS pain rating at study entry

was 65.00. In the 2001 comparative trial, 43 subjects received the active Erchonia® EVRL red diode only procedure administration.

Each subject received a single 13-minute active procedure administration with the Erchonia® EVRL at the investigator's test site as in the 2001 trial, differing only in dual-diode (red and violet) versus single-diode (red only) application, respectively.

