The clinical study that supported clearance of K191257 and K212595 was a single arm (active treatment only), historical comparative design to demonstrate non-inferiority of the standard Erchonia red laser therapy when used in simultaneous combination with violet laser therapy compared with application of the standard Erchonia red laser therapy protocol alone in the temporary reduction of neck and shoulder pain of musculoskeletal origin. The historical comparative active data set for that clinical study used for non-inferiority analysis was the results from the Erchonia® red diode therapy only active subject group attained in the 2001 trial whose results successfully supported 510(k) clearance (K012580) of application of red laser light therapy only for the identical indication. This same historical comparative active data set will be used as the historical comparative Erchonia red laser therapy only active treatment data set for the current proposed clinical study.

SUBJECT GROUP

There will be a single subject group treated in this study. All subjects will receive the active study treatment with the blue laser therapy using the Erchonia® PPL first followed sequentially with the standard Erchonia red laser therapy (*Erchonia XLR8, FDA cleared under K211186*)

Comparative subject data for the red diode alone procedure administration will be taken from the Erchonia 2001 study whose results supported FDA market clearance for K012580.

BLINDING

As all subjects in this study will receive active treatment administrations with the Erchonia® PPL and the Erchonia XLR8, neither subjects nor investigators will be blinded. The statistician analyzing the study results will however be blinded with respect to study success analysis. The data from this combined laser therapy study and the retrospective comparative data from the 2001 red diode only study will be deidentified and presented to the study statistician as 'Group A' and 'Group B'. The statistician will not be aware of which group – A or B – contains the current combined laser therapy data and which contains the retrospective comparative red diode only data.

RANDOMIZATION

As this study is a single treatment group study, randomization to treatment group is not applicable. Therefore, this is a non-randomized trial.

SUBJECTS

Subject Sample

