Subjects will be males and females 22 years or older who present with chronic (30 consecutive days or longer) neck and/or shoulder pain diagnosed as being of musculoskeletal origin (osteoarthritis, chronic muscle spasm, cervical and thoracic spine sprain strain) and with a self-reported pain level of 50 or greater on the 0 to 100 VAS.

Sample Size

There will be 43 qualified subjects enrolled in this study.

Rationale for Sample Size

Sample size is determined to be identical to that of subjects enrolled in the active treatment group that forms the comparative data reference group in this study.

Recruitment

Subjects will be recruited from among:

- (i) The Principal Investigator's/test site's pool of existing and new patients
- (ii) Referrals from other suitable medical clinics and professionals
- (iii) Subjects who respond to the recruitment materials shown in **Appendix A**.

Compensation

A subject will not receive financial or any other form of compensation to participate in this clinical study. However, he or she will also not be charged for the cost of the study treatment with the Erchonia lasers or for the cost of any other directly-related evaluations or measurements that occur as a directly-associated part of his or her participation in the study.

STUDY PROCEDURE

STUDY TEST BATTERY

The following are the study measurement and assessment tools to be used and the variables to be recorded in this clinical study. At each evaluation point, the precise tools and variables that will be employed will be specified.

QUALIFICATION EVALUATION TOOL

PHYSICAL EXAMINATION

- (i) Inspection: Manipulation of the neck, shoulders, and cervical spine to evaluate for knots (muscle spasms), tightness, swelling, osteophytes, etc.
- (ii) Palpation Assessment: Physical assessment of the bony and soft tissues of the neck, shoulder, and cervical spine through touch with the pads of the fingers, to evaluate for muscle tightness and knotting, trigger points that cause pain and possibly also radiating pain.

BASELINE VARIABLES

NECK/SHOULDER PAIN VARIABLES

- (i) Location of pain: right side/left side/back of neck; right/left shoulder
- (ii) Duration of pain: months/years since onset of first episode of neck/shoulder pain

CONCOMITANT MEDICATION AND THERAPY USE

- (i) Over the counter and prescription medications currently used to relieve neck/shoulder pain, including duration, dosage, and frequency of use

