The primary efficacy outcome measure for this clinical study is identical to that of the comparative reference study and is defined as the change in subject self-reported Visual Analog Scale (VAS) pain rating from baseline to study endpoint evaluation, with study endpoint defined as within 3 minutes of completion of the study single sequential treatment administration with the Erchonia® PPL blue laser therapy followed by the standard Erchonia red laser therapy administered using the Erchonia® XLR8.

Individual Subject Success Criteria

individual subject success criteria is defined as a 30% or greater decrease in self-reported neck and shoulder pain rating on the 0-100 VAS at study endpoint relative to baseline.

Overall Study Success Criteria.

Overall study success criteria is defined as at least 65%±5% of subjects in the current study meeting the study individual subject success criteria.

Justification for Study Success Criteria

The clinical relevance and justification of the individual and overall study success criteria is as follows:

- This study is a non-inferiority study, such that the research hypothesis is that the sequential combination therapy with the Erchonia® PPL blue laser and the standard Erchonia red laser therapy is either equivalent to or superior to the standard Erchonia red diode only therapy in effecting a clinically meaningful reduction in neck and shoulder pain of musculoskeletal origin, based upon the data attained from the red diode only clinical trial conducted in 2001 whose results successfully supported 510(k) clearance of application of the PL3000 red diode only for the identical indication being sought through the results of this clinical trial.
- The individual subject success criteria in this clinical study is identical to that of the comparative reference study.
- The overall study success criteria in this clinical study is based on the actual proportion of individual subject successes attained during the comparative reference trial for the active red diode treatment group, of 65%. The $\pm 5\%$ is the selected equivalence margin (δ), the maximally clinically acceptable difference for which the range of values (60% to 70%) for which the efficacies are “close enough” to be considered equivalent.
- Non-inferiority will be established if the proportion of subjects who attain the individual subject success criteria is no more than 5% less than the reference subject group (i.e. no less than 60%).

Hypotheses

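### The 2001 red-only success rate, 28 of 43, is treated as a known 65%, so a claim of non-inferiority within 5 points leaves out the reference group's sampling error

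*Combined protocol and SAP*

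**What the plan says.** The purpose and both hypotheses are comparative: the blue-then-red sequence against red laser alone. Under Study Design, the comparator is the active arm of the 2001 trial: "This same historical comparative active data set will be used as the historical comparative Erchonia red laser therapy only active treatment data set". Under Blinding, both data sets go to the statistician, coded as Group A and Group B.

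Under Justification for Study Success Criteria, the bar is "based on the actual proportion of individual subject successes attained during the comparative reference trial for the active red diode treatment group, of 65" percent. The 5 points "is the selected equivalence margin (δ), the maximally clinically acceptable difference". Subtracting one from the other gives the 60% threshold. Under Hypotheses, the null is P ≤ 60%, where P is the responder rate in the current study; the red-only rate does not appear as a parameter.

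The source of the 65% is item 1 of the supporting clinical data: "65.1% of actively treated subjects attained individual success compared with 11.6% of control (placebo) subjects". Item 2 gives the size of that group: "43 subjects received the active Erchonia® EVRL red diode only procedure administration". The current study is the same size ("There will be 43 qualified subjects enrolled in this study"), for the stated reason that "Sample size is determined to be identical to that of subjects enrolled in the active treatment group that forms the comparative data reference group".

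No confidence interval, standard error or two-sample comparison is specified for the responder rate, and no alpha is attached to the primary criterion. The only between-group efficacy analysis is the t-test on mean VAS change, under Change Scores, which is described as supportive.

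**The concern.** A statement that the new regimen is at most 5 points worse than red laser alone is a statement about a difference between two rates. Here both rates come from samples of 43, so both contribute sampling error. The plan replaces one of them with a constant. Five points is about two subjects in 43 (0.05 × 43 = 2.15), so the margin is small beside the uncertainty that has been dropped.

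What is at stake is the wording of the primary conclusion. The study could meet its criterion and be reported as non-inferior to red laser alone, although the data remain compatible with a deficit several times the margin. The rule would not show this, because it compares one observed percentage with a fixed number.

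**Working it through.** **Inputs.** Reference rate 65.1% active and 11.6% placebo (supporting clinical data, item 1); reference group 43 (item 2); current N 43 (Sample Size); margin 5 points and bar 60% (Justification for Study Success Criteria). I assume that all 43 current subjects have an observed response and that the ITT and per-protocol sets coincide.

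**Reproducing the plan's figure.** 28/43 = 65.1%; 5/43 = 11.6%; the difference is 53.5 points, as stated. The smallest count at or above 60% of 43 (25.8) is 26, and 26/43 = 60.5%. So the operative rule is 26 or more responders.

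**Precision of the reference.** The exact (Clopper-Pearson) 95% interval for 28/43 is 49.1% to 79.0%. Its standard error is √(0.651 × 0.349 / 43) = 0.0727, so the reference alone carries about 1.96 × 7.27 = ±14.2 points.

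**The comparison at a just-passing result.** The Newcombe interval combines the two Wilson intervals: 26/43, 0.456 to 0.736; 28/43, 0.502 to 0.776. With d = 0.6047 - 0.6512 = -0.0465:

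- lower = -0.0465 - √[(0.6047 - 0.4558)² + (0.7758 - 0.6512)²] = -0.241
- upper = -0.0465 + √[(0.7363 - 0.6047)² + (0.6512 - 0.5017)²] = +0.153

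The interval is -24 to +15 points. At equal observed rates (28 against 28) the same formula gives ±19.5 points, about four times the margin.

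**Operating characteristics.** Probability of success is P(X ≥ r), X binomial with n = 43. The written rule has r = 26. For contrast, an exact one-sided test of P ≤ 60% at 0.05 (an assumed alpha, since the plan gives none) has r = 32, with actual size 0.035.

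| True red rate | Regimen 10 points worse, written rule | Regimen 10 points worse, exact test | Regimen equal to red, written rule |
|---|---|---|---|
| 55% | 0.030 | <0.001 | 0.287 |
| 65% | 0.287 | 0.007 | 0.785 |
| 70% | 0.541 | 0.035 | 0.934 |
| 75% | 0.785 | 0.127 | 0.989 |

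All four red rates lie inside the 49.1% to 79.0% interval. Averaged over a Jeffreys posterior for the red rate given 28/43, a regimen 10 points worse passes the written rule with probability about 0.34. That posterior puts about 24% on a red rate of 70% or more and about 7% on 75% or more.

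**What the comparative claim would need.** Two-sided 95% lower limit for the difference, against 28/43:

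| Current responders | Newcombe | Miettinen-Nurminen |
|---|---|---|
| 34/43 (79.1%) | -4.998 points | -5.2 points |
| 35/43 (81.4%) | -2.5 points | -2.6 points |

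So the requirement is 34 responders by Newcombe or 35 by Miettinen-Nurminen, against 26 under the written rule. P(X ≥ 35) is 0.015 at a true rate of 65% and 0.22 at 75%.

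**The case against.** The strongest reply is that this is an openly declared single-arm historical comparison, modelled on a design that the protocol says supported an earlier clearance, and that a fixed performance goal is a recognised single-arm method. That stands as far as the choice of design goes. It does not make a 43-subject estimate exact, and the protocol attaches a non-inferiority conclusion to the bar, not a performance-goal conclusion.

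A second reply is that the planned two-sample t-test uses the variance of both groups. It does, but it concerns mean VAS change, has no margin, and cannot alter the responder criterion.

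A reader might infer that a regimen twice the margin worse than red will pass with high probability. The figures do not support that as a general statement. At the point estimate of 65% the probability is 0.287; it reaches 0.785 only if the true red rate is 75%, in the upper part of the interval. Much of it also comes from the separate lack of a test or alpha: an exact one-sided 0.05 test that still treated 65% as known would cut 0.541 and 0.785 to 0.035 and 0.127. Nor is the rule lenient in one direction only, since an equally good regimen would usually fail if red is truly 55%.

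**Conclusion.** The point holds in this form: the primary criterion ignores the sampling error of its reference, and so cannot support a claim of non-inferiority to red laser alone within 5 points. The main evidence is the interval of -24 to +15 points at a just-passing result and ±19.5 points at equal observed rates. Neither depends on an assumed true red rate. The pass probabilities do depend on one and should be quoted together as 0.29, 0.54 and 0.785 for 65%, 70% and 75%, with the note that part of their size belongs to the missing test.

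Adding a test of P ≤ 60% would be worthwhile but would not cure this defect, because the reference would remain a constant.

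The intervals cover sampling error only. The 2001 trial was double-blind and placebo-controlled, and the current study is open-label. Any resulting bias is a separate matter that the documents do not allow one to quantify, and it is not part of the figures above.

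**What to change.** In the statistical analysis plan:

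1. Describe 60% as a fixed performance goal derived from the 2001 point estimate.
2. Report the difference in responder rate, current minus 2001 active, from the Group A/B data, with one pre-named two-sided 95% confidence interval, for example Miettinen-Nurminen. Name only one method: at 34/43, Newcombe and Miettinen-Nurminen give opposite answers.
3. Conclude non-inferiority to red laser alone only if the lower limit exceeds -5 points (35/43 by Miettinen-Nurminen, 34/43 by Newcombe). Otherwise limit the conclusion to whether the performance goal was met.

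The edit itself is cheap: SAP wording and one calculation on data that the statistician will already hold. The real cost is a weaker conclusion. At N = 43 the 5-point comparative claim has a probability of about 0.015 at a true rate of 65%. Enlarging the current study alone would not rescue it at equal observed rates, because the 2001 group contributes about ±14 points whatever the new sample size. If the sponsor wants the comparative claim to be attainable, the margin, the design or the claim itself would have to be reconsidered, which is more than a wording change.

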Study primary outcome measure was change in Visual Analog Scale (VAS) neck and shoulder pain rating from baseline to study endpoint evaluation. Individual subject success criteria was established as a 30% or greater decrease in VAS rating at endpoint relative to baseline. The study was pre-established as a non-inferiority study (equivalency or superiority) of the EVRL in red/violet diode combination therapy compared to the red diode only therapy as based upon the comparative data from the 2001 trial. Overall study success criteria was established as 65±5% of individual subject successes in the current trial. Seventy-five per cent (75%) of subjects in this dual diode violet/red laser study attained individual subject success compared with 65.1% of actively treated subjects in the 2001 trial, exceeding the overall study success criteria by 5%. The 29.80-point mean decrease (from 65.00 to 35.20) in neck and shoulder VAS pain rating from study Baseline to Endpoint for subjects in the violet/red laser study was comparable to (slightly above) the respective 29.02-point mean decrease (from 60.21 to 31.19) for the 2001 Active study subjects. As in the 2001 red laser only study, no adverse or other safety events were reported or recorded across study duration.

It was concluded that the application of simultaneous violet and red laser light was non-inferior to the application of red laser light alone in providing adjunctive temporary relief of minor chronic neck and shoulder pain of musculoskeletal origin.

3. The above two Erchonia-sponsored clinical trial outcomes, in addition to the below two Erchonia-sponsored clinical trial outcomes provided primary support for clearance of the indication for '*adjunctive use in providing temporary relief of nociceptive musculoskeletal pain*' for the respective light therapy devices:

➤ **CHRONIC LOW BACK PAIN:**

➤ **CHRONIC PLANTAR FASCIITIS HEEL PAIN:**

STUDY JUSTIFICATION

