- *Null Hypothesis:* Sequential treatment application of the Erchonia® PPL blue laser therapy followed by the standard Erchonia® red laser therapy using the XLR8 is inferior to treatment application of the Erchonia red laser therapy alone in reducing neck and shoulder nociceptive pain of musculoskeletal origin to the effect of 60% or fewer subjects attaining a 30% or greater reduction in neck and shoulder pain at study endpoint evaluation relative to baseline.

$H_0: P \leq 60\%$; where P = individual subject responder rate

- *Alternative Hypotheses:* Sequential treatment application of the Erchonia® PPL blue laser therapy followed by the standard Erchonia® red laser therapy using the XLR8 is NOT inferior to (i.e., is equivalent to or superior to) treatment application of the Erchonia red laser therapy only in reducing neck and shoulder nociceptive pain of musculoskeletal origin to the effect of greater than 60% of subjects attaining a 30% or greater reduction in neck and shoulder pain at study endpoint evaluation relative to baseline.

$H_1: P > 60\%$; where P = individual subject responder rate

Evaluation Time Point

Study endpoint evaluation was preestablished as occurring immediately (within 3 minutes) following completion of administration of the second component of the sequential study treatment with the standard Erchonia® red light laser device. Study primary success analysis is preestablished at study endpoint relative to baseline, identically to that in the 2001 reference comparative study.

Change Scores

- T-test analysis of the difference in the mean change in VAS levels from baseline to endpoint between the dual-diode and red only diode treatment administration groups. Significance levels will be considered at the $p < 0.05$ level.
- A t-test for two independent sample will be performed to evaluate the significance of the difference in the mean change in VAS pain scores from baseline to endpoint evaluation between the two study groups to evaluate for equivalency to support the support the conclusion of the proportion of successes evaluation. Significance levels will be considered at the $p < 0.05$ level.

SECONDARY EVALUATIONS

The following secondary evaluations will be performed on the per protocol study data set only. As no claims are intended to be made based on secondary measures, the findings will be presented through descriptive analysis and qualitative trending only, without evaluation for or claims of statistical significance.

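### Non-inferiority is declared from the observed responder rate alone (26 or more of 43), so the stated rule does not test the stated null hypothesis of 60% or less

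*Combined protocol and SAP*

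**What the plan says.** All places are in the combined protocol and SAP.

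- **Hypotheses.** The null is that the combined regimen is inferior, "to the effect of 60% or fewer subjects attaining a 30% or greater reduction", written as P ≤ 60%. The alternative is P > 60%.
- **Justification for Study Success Criteria.** Non-inferiority is established if the success proportion "is no more than 5% less than the reference subject group (i.e. no less than 60" per cent).
- **Overall Study Success Criteria.** "Overall study success criteria is defined as at least 65%±5% of subjects in the current study" must meet the individual criterion, a fall of 30% or more on the pain scale.
- **Populations Examined.** ITT is primary and PP supportive; non-inferiority requires the two to agree.
- **Handling of Missing Data.** Multiple imputation, with the exact method chosen after the study is complete.
- **Change Scores.** A two-sample t-test on mean change in pain score at p < 0.05, to support the conclusion drawn from the proportions.
- **Sample Size.** "There will be 43 qualified subjects enrolled in this study". The rationale is only that "Sample size is determined to be identical to that of subjects enrolled in the active treatment group" of the reference study. No power or type I error is given.

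**The concern.** A null and an alternative hypothesis are written down for the responder rate, but the rule for rejecting the null is that the estimate itself reaches the null boundary. A sample proportion falls on either side of its true value about equally often, so a regimen sitting exactly on the boundary passes roughly half the time. The SAP names no test, significance level or confidence limit for this proportion that would reduce that error.

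The results are meant to support a 510(k) submission. A statement that non-inferiority has been shown would ordinarily be read as excluding, at a conventional error rate, a responder rate at or below 60%. This rule does not do that.

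**Working it through.** **Inputs.** n = 43 (Sample Size). Null boundary p0 = 0.60 (Hypotheses). Cut-off: observed proportion at least 60% (Justification for Study Success Criteria). Reference: "65.1% of actively treated subjects attained individual success compared with 11.6% of control (placebo) subjects", and "In the 2001 comparative trial, 43 subjects received the active" treatment (Supporting Erchonia Corporation Clinical Data, items 1 and 2).

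**The plan's own figures.** 28/43 = 65.1%, which matches the reference rate. The 43 is copied from the historical group, so there is no power calculation to reproduce.

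**Step 1: cut-off.** 0.60 × 43 = 25.8, so 26 or more successes are needed (26/43 = 60.5%).

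**Step 2: pass probability with ITT and PP identical.** With X ~ Binomial(43, p), P(X ≥ 26) = Σ C(43, x) p^x (1 − p)^(43 − x), summed from x = 26 to 43:

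| True rate | P(pass) |
|---|---|
| 50% | 0.111 |
| 55% | 0.287 |
| 60% (null boundary) | 0.541 |
| 65% | 0.785 |

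**Step 3: requiring ITT and PP to agree.** Assume d subjects leave PP at random and all 43 ITT outcomes are observed. Let X ~ Binomial(43 − d, 0.60) count successes in PP and Y ~ Binomial(d, 0.60) those among subjects who left. Passing needs X/(43 − d) ≥ 0.60 and X + Y ≥ 26.

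| d | PP size | PP cut-off | P(both pass) at 60% |
|---|---|---|---|
| 0 | 43 | 26 | 0.541 |
| 1 | 42 | 26 | 0.467 |
| 2 | 41 | 25 | 0.497 |
| 3 | 40 | 24 | 0.515 |
| 4 | 39 | 24 | 0.466 |
| 5 | 38 | 23 | 0.490 |
| 6 | 37 | 23 | 0.436 |
| 7 | 36 | 22 | 0.465 |

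The range for d = 1 to 7 is about 0.44 to 0.52.

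**Step 4: what a just-passing result shows.** The exact (Clopper-Pearson) 95% interval for 26/43 is 44.4% to 75.0%.

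**Step 5: a rule that does test the null.** The smallest count with P(X ≥ k | 0.60) ≤ 0.025 at n = 43 is k = 33 (76.7%). Its actual size is 0.016 and its exact 95% interval is 61.4% to 88.2%. Power, P(X ≥ 33), is 0.070 at a true 65%, 0.215 at 70%, 0.477 at 75% and 0.771 at 80%. At one-sided 0.05 the cut-off would be 32/43, with size 0.035 and power 0.127 at 65%.

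**Step 6: sample size for 80% power at a true 65%.** n = [(z_{1−α}√(0.60 × 0.40) + z_{0.80}√(0.65 × 0.35)) / 0.05]². At one-sided 0.025 this is [(1.960 × 0.4899 + 0.8416 × 0.4770) / 0.05]², about 742. At one-sided 0.05 it is about 583.

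**The case against.** Several points can be made for the plan or against a harsher reading.

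- **The ITT/PP agreement rule is part of the decision.** This stands. A reader might infer an unconditional type I error above one half, but 0.54 applies only when the two sets coincide. Under the assumption in step 3, only one of the seven cases with dropout exceeds one half. The lower figures are still far above any conventional level.
- **The rule does carry information.** This also stands. A reader might infer that a positive result would be worthless. Pass rates of 0.785 at 65%, 0.287 at 55% and 0.111 at 50% show that the rule discriminates, though weakly near 60%.
- **The threshold is settled.** Largely so. The phrase with ±5% could suggest 60%, 65% or 70%, and the account of the earlier violet/red study describes 75% as "exceeding the overall study success criteria by 5" percentage points, which implies 70%. But the current SAP states 60% explicitly in both the justification and the hypotheses, and a summary of an earlier result does not override that. What remains is loose wording.
- **Exactly 60% counts as inferior in the null and as passing in the rule.** At n = 43 this changes nothing, because 25.8 is not a whole number and both versions give 26. It could matter only for a denominator such as 40, where 24/40 is exactly 60%.
- **A t-test at p < 0.05 is planned.** It concerns mean pain change, tests for a difference, and is not in the non-inferiority rule, so it does not control this error.
- **The design was accepted before.** The protocol says so, but that does not alter the rule's error rate.

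**Conclusion.** The concern holds. The decision rule does not test the hypothesis that the SAP states. At a true rate of 60% it declares non-inferiority with probability 0.54 if ITT and PP are the same 43 subjects with complete data, and about 0.44 to 0.52 if 1 to 7 subjects leave PP at random. At a true 55%, with identical sets, the figure is 0.29. A passing result does not exclude responder rates below 60%. The documents do not support going further, to an error rate that always exceeds one half, a result without information, or a threshold that cannot be identified.

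The figures rest on independent binomial outcomes, 43 evaluable subjects in ITT, and the plan's own treatment of the 65% reference as fixed. Departures from PP that depend on outcome, or imputed ITT outcomes, would change the joint figures.

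**What to change.** **Preferred.** Conclude non-inferiority only if the lower limit of the two-sided 95% confidence interval for the responder rate exceeds 60% in both ITT and PP.

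- With complete data, use the exact (Clopper-Pearson) limit at the actual denominator: 33/43, or 32/42, 32/41 or 31/40 for a smaller PP set. A single count cannot serve both sets if they differ in size.
- When ITT outcomes are multiply imputed there may be no single count. Use a limit combined across imputations by Rubin's rules, with the method fixed in the SAP before the data are seen.
- State the power at n = 43: 7% at a true 65%, 21% at 70%, 48% at 75% and 77% at 80%.

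The two-sided 95% level is a proposal, since the SAP sets none for this endpoint. The sponsor should choose a level and write it down.

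**Alternative.** If 26/43 is kept, label it a descriptive performance goal, state its pass rate of roughly 44% to 54% at a true 60%, and remove the null and alternative hypotheses and the claim that non-inferiority is established.

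**Wording clean-up only.** Replace the overall success criterion's ±5% phrase with the single 60% threshold used elsewhere in the SAP.

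**Cost.** The changes are to protocol and SAP text, and no new data are needed. The real cost of the preferred rule is that a 43-subject trial is unlikely to meet it unless the true rate is well above 65%. By the approximation in step 6, 80% power at 65% would need about 742 subjects, or 583 at one-sided 0.05.
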